**Document History**

Document	Version Date
Original protocol	30 November 2022

## 1. PROTOCOL SUMMARY

### 1.1. Synopsis

**Protocol Title:** A Phase 1, Open-Label, 2-Period, 2-Sequence, Crossover Study to Compare the Single-Dose Pharmacokinetics of 2 Different Formulations of PF-07081532 Administered Orally to Adult Participants Who Are Overweight or Obese

**Brief Title:** Phase 1 Study to Compare PK of Single Oral Doses of 2 Different PF-07081532 Formulations in Adult Participants Who Are Overweight or Obese

### Regulatory Agency Identification Number(s):

US IND Number:	CCI [REDACTED]
EudraCT/EU CT Number:	Not Applicable
ClinicalTrials.gov ID:	Not Available
Pediatric Investigational Plan Number:	Not Applicable
Protocol Number:	C3991010
Phase:	1

### Rationale:

The purpose of the study is to evaluate the relative bioavailability following oral administration of 2 formulations of PF-07081532. In Periods 1 and 2, the PK of the formulation projected to be used in future clinical studies (PF-07081532 80 mg immediate release tablet, Formulation B) will be compared with the PK of the current formulation (PF-07081532 20 mg immediate release tablet + 60 mg immediate release tablet, Formulation A) in the fasted state in adult participants who are overweight or obese.

### Objectives and Endpoints:

Objectives	Endpoints
Primary:	Primary:

To compare the relative bioavailability of PF-07081532 following administration of a single oral dose of Formulation B (Test) compared to Formulation A (Reference) administered in the fasted state to adult participants who are overweight or obese.

	

Plasma: PF-07081532 <math>AUC_{inf}</math> (as data permit, otherwise <math>AUC_{last}</math>) and <math>C_{max}</math> for Formulations A and B.

Secondary:	Secondary:

To evaluate the safety and tolerability of a single oral dose of PF-07081532 administered in the fasted state to adult participants who are overweight or obese.

	

Assessment of treatment emergent AEs, clinical laboratory abnormalities, vital signs, ECG parameters.

### **Overall Design:**

This is a randomized, open-label, single dose, 2-period, 2-sequence, crossover study. Participants will be screened for participation in this study within 28 days before dosing in Period 1 to confirm that they meet the inclusion/exclusion criteria for this study. A minimum of 6 days between the single 80 mg doses (80 mg immediate release tablet for Formulation B, 20 mg immediate release tablet + 60 mg immediate release tablet for Formulation A) administered in each period will be employed. The expected duration of participation from Screening to the Follow-up telephone contact will be approximately 10 weeks.

### **Number of Participants:**

Approximately 20 participants will be enrolled to ensure at least 14 evaluable participants with PK data.

Note: "Enrolled" means a participant's, or their legally authorized representative's, agreement to participate in a clinical study following completion of the informed consent process and randomization/assignment to study intervention. A participant will be considered enrolled if the informed consent is not withdrawn prior to participating in any study activity. Potential participants who are screened for the purpose of determining eligibility for the study, but do not participate in the study, are not considered enrolled, unless otherwise specified by the protocol.

### **Study Population:**

Inclusion and exclusion criteria are listed below:

#### **Inclusion Criteria**

Participants are eligible to be included in the study only if all of the following criteria apply:

1. Male and female participants must be at least 18 years of age, inclusive, at the time of signing the ICD.
2. Male and female participants who are healthy as determined by medical evaluation including medical history, physical examination, laboratory tests, vitals and ECGs.
3. Participants who are willing and able to comply with all scheduled visits, treatment plan, laboratory tests, lifestyle considerations, and other study procedures.
4. A total body weight  $>50$  kg (110 lb) and BMI of 25.0 to  $<34.9$  kg/m^2, inclusive, at the screening visit.
5. Capable of giving signed informed consent as described in Appendix 1, which includes compliance with the requirements and restrictions listed in the ICD and in this protocol.

## **Exclusion Criteria**

Participants are excluded from the study if any of the following criteria apply:

1. Evidence or history of clinically significant hematological, renal, endocrine, pulmonary, gastrointestinal, cardiovascular, hepatic, psychiatric, neurological, or allergic disease (including drug allergies, but excluding untreated, asymptomatic, seasonal allergies at the time of dosing).
  - Any condition possibly affecting drug absorption (eg, prior bariatric surgery, gastrectomy, ileal resection).
  - History of HIV infection, hepatitis B, or hepatitis C; positive testing at screening for HBsAg, HBcAb, HCVAb or HIV. Hepatitis B vaccination is allowed.
2. Personal or family history of MTC or MEN2 or pancreatitis, or participants with suspected MTC per the investigator's judgement.
3. Other medical or psychiatric condition including recent (within the past year) or active suicidal ideation/behavior or laboratory abnormality that may increase the risk of study participation or, in the investigator's judgment, make the participant inappropriate for the study.
4. Use of prescription or nonprescription drugs and dietary and herbal supplements within 7 days or 5 half-lives (whichever is longer) prior to the first dose of study intervention.
5. In females, current use of hormone replacement therapy or oral/injectable contraceptives containing ethinyl estradiol.
6. Previous administration with an investigational product (drug or vaccine) within 30 days (or as determined by the local requirement) or 5 half-lives (whichever is longer) preceding the first dose of study intervention used in this study. Investigational products which are strong CYP3A inducers or time-dependent inhibitors are prohibited within 14 days plus 5 half-lives or 30 days (whichever is longer) prior to the dose of study intervention.
7. Known prior participation (ie, randomized and received at least 1 dose of investigational product) in a study involving PF-07081532 or known intolerance to a GLP-1R agonist.
8. A positive urine drug test.
9. Using a properly sized and calibrated BP cuff, screening supine BP  $\geq$ 140 mm Hg (systolic) or  $\geq$ 90 mm Hg (diastolic) following at least 5 minutes of supine rest. If BP is  $\geq$ 140 mm Hg (systolic) or  $\geq$ 90 mm Hg (diastolic) the BP should be repeated 2 more

times and the average of the 3 BP values should be used to determine the participant's eligibility.

10. Baseline 12-lead ECG that demonstrates clinically relevant abnormalities that may affect participant safety or interpretation of study results (eg, baseline QTcF interval  $>450$  msec, complete LBBB, signs of an acute or indeterminate age myocardial infarction, ST-T interval changes suggestive of myocardial ischemia, second or third degree AV block, or serious bradyarrhythmias or tachyarrhythmias). If the baseline uncorrected QT interval is  $>450$  msec, this interval should be rate corrected using the Fridericia method and the resulting QTcF should be used for decision making and reporting. If QTcF exceeds 450 msec, or QRS exceeds 120 msec, the ECG should be repeated 2 more times and the average of the 3 QTcF or QRS values should be used to determine the participant's eligibility. Computer interpreted ECGs should be overread by a physician experienced in reading ECGs before excluding participants.
11. Participants with ANY of the following abnormalities in clinical laboratory tests at screening, as assessed by the study-specific laboratory and confirmed by a single repeat test, if deemed necessary:
  - AST or ALT level  $\geq 1.25 \times$  ULN;
  - Total bilirubin level  $\geq 1.5 \times$  ULN; participants with a history of Gilbert's syndrome may have direct bilirubin measured and would be eligible for this study provided the direct bilirubin level is  $\leq$  ULN;
  - HbA1c  $\geq 6.5\%$ ;
  - Fasting blood glucose  $\geq 126$  mg/dL (7 mmol/L);
  - Calcitonin  $>$  ULN;
  - eGFR  $<60$  mL/min/1.73 m^2 as calculated by the CKD-EPI equation.
12. History of alcohol abuse or binge drinking and/or any other illicit drug use or dependence within 6 months of Screening. Binge drinking is defined as a pattern of 5 (male) and 4 (female) or more alcoholic drinks in about 2 hours. As a general rule, alcohol intake should not exceed 14 units per week (1 unit = 8 ounces (240 mL) beer, 1 ounce (30 mL) of 40% spirit or 3 ounces (90 mL) of wine).
13. Participants with current use of tobacco and/or nicotine containing products exceeding equivalent of 5 cigarettes per day.
14. Blood donation (excluding plasma donations) of approximately 1 pint (500 mL) or more within 60 days prior to dosing.

15. Unwilling or unable to comply with the criteria in the Lifestyle Considerations section of this protocol.
16. Investigator site staff or Pfizer employees directly involved in the conduct of the study, site staff otherwise supervised by the investigator, and their respective family members.
17. History of sensitivity to heparin or heparin induced thrombocytopenia.

**Study Arms and Duration:**

Study Intervention(s)		
Intervention Name	PF-07081532	
Arm Name (group of participants receiving a specific treatment or no treatment)	Sequence 1	Sequence 2
Unit Dose Strength(s)	20 mg 60 mg 80 mg	
Route of Administration	Oral	
Use	Experimental	
IMP or NIMP/AxMP	IMP	

Study Arm(s)		
Arm Title	Sequence 1	Sequence 2
Arm Type	Experimental	Experimental
Arm Description	Participants will receive a single dose of PF-07081532 20 mg immediate release tablet + 60 mg immediate release tablet (Formulation A) on Period 1 Day 1, and receive a single dose of PF-07081532 80 mg immediate release tablet (Formulation B) on Period 2 Day 1, with a minimum of 6 days between 2 doses.	Participants will receive a single dose of PF-07081532 80 mg immediate release tablet (Formulation B) on Period 1 Day 1, and receive a single dose of PF-07081532 20 mg immediate release tablet + 60 mg immediate release tablet (Formulation A) on Period 2 Day 1, with a minimum of 6 days between 2 doses.

**Statistical Methods:**

A sample size of 14 participants will provide adequate precision to estimate the relative bioavailability of PF-07081532.

### **PK parameters:**

Plasma PK parameters of PF-07081532 will be derived (as data permit) from the concentration-time data using standard noncompartmental methods. Actual PK sampling times will be used in the derivation of PK parameters. In the case that actual PK sampling times are not available, nominal PK sampling time will be used in the derivation of PK parameters.

Natural log transformed  $AUC_{\text{inf}}$  (if data permit),  $AUC_{\text{last}}$  and  $C_{\text{max}}$  will be analyzed using a mixed effect model with sequence, period and treatment as fixed effects and participant within the sequence as a random effect. Estimates of the adjusted mean differences (Test-Reference) and corresponding 90% CIs will be obtained from the model. The adjusted mean differences and 90% CIs for the differences will be exponentiated to provide estimates of the ratio of adjusted geometric means (Test/Reference) and 90% CI for the ratios. Formulation A (PF-07081532 20 mg + 60 mg) will be the Reference treatment while Formulation B (PF-07081532 80 mg) will be the Test treatment.

PK parameters, including plasma  $AUC_{\text{inf}}$ ,  $AUC_{\text{last}}$ ,  $C_{\text{max}}$ ,  $T_{\text{max}}$ ,  $t_{1/2}$ ,  $CL/F$ , and  $V_z/F$  of PF-07081532 will be summarized descriptively by treatment. For  $AUC_{\text{inf}}$ ,  $AUC_{\text{last}}$  and  $C_{\text{max}}$ , a listing of the individual participant ratios (Test/Reference) will be provided. Box and whisker plots for  $AUC_{\text{inf}}$ ,  $AUC_{\text{last}}$  and  $C_{\text{max}}$ , will be plotted by treatment.

The plasma concentrations of PF-07081532 will be listed and descriptively summarized by nominal PK sampling time and treatment. Individual participant, as well as mean and median profiles of the plasma concentration time data will be plotted by treatment using actual (for individual) and nominal (for mean and median) times respectively. Mean and median profiles will be presented on both linear and semi-log scales.

### **Safety:**

Safety data will be presented in tabular and/or graphical format and summarized descriptively, where appropriate.

### **Ethical Considerations:**

A single dose of PF-07081532 is not expected to provide any clinical benefit to study participants. Results from this study will be used to evaluate the effect of formulation on the relative bioavailability of PF-07081532.

### **1.2. Schema**

Not applicable.

### 1.3. Schedule of Activities

The SoA table provides an overview of the protocol visits and procedures. Refer to the **STUDY ASSESSMENTS AND PROCEDURES** section of the protocol for detailed information on each procedure and assessment required for compliance with the protocol.

The investigator may schedule visits (unplanned visits) in addition to those listed in the SoA table, in order to conduct evaluations or assessments required to protect the well-being of the participant.

**SoA-Table 1. Study Schedule of Assessment**

Visit Identifier Abbreviations used in this table may be found in Appendix 10 .	Screening	Periods 1 and 2					ET	Follow -Up	Notes
Days Relative to Day 1	Day -28 to Day -2	Day -1 (Period 1 Only)	Day 1	Day 2	Day 3	Day 4	Day 5		28-35 days
Hours After Dose			0	48	72	96			
Informed consent	X								
Demography	X								
COVID-19 assessment		See Notes							

• All screening should be done <math>\leq</math>28 days before the first dose.

• Day relative to start of study intervention (Day 1).

• Follow-up may occur via telephone contact and must occur 28 to 35 days after administration of the final dose of study intervention.

Review of eligibility criteria	X	X							
Inpatient stay at Clinical Research Unit		X	→	→	→	→	X		
Medical history	X	X							

**SoA-Table 1. Study Schedule of Assessment**

Visit Identifier Abbreviations used in this table may be found in Appendix 10 .	Screening	Periods 1 and 2					ET	Follow -Up	Notes
Days Relative to Day 1	Day -28 to Day -2	Day -1 (Period 1 Only)	Day 1	Day 2	Day 3	Day 4	Day 5		28-35 days
Hours After Dose		0	48	72	96				
Physical exam	X	X					X		
 
At screening: height & body weight only.
 
Complete PE at Day -1 of Period 1; otherwise brief physical exam for findings during previous PE or new/open AEs at PI discretion.
 

Contraception use (females only)	X	X					X	X	
 
WOCBP only
 

Prior/concomitant treatments	X	X					X	X	
Single, supine 12-lead ECG	X		X				X	X	
 
Day 1 ECG: to be conducted pre-dose
 
Day 5 ECG: in Period 2 only.
 

Single, supine vital sign assessment (BP and pulse rate)	X		X				X	X	
 
Day 1 assessment: to be conducted pre-dose
 
Day 5 assessment: in Period 2 only.
 

Serious and non-serious adverse event monitoring	X	X	→	→	→	→	X	X	
Study intervention administration			X						
 
Following ≥10-hr fast; and for Period 2, a minimum 6-day interval from dosing in the previous period.
 

Urine drug test	X	X							
Urinalysis (and microscopy, if needed)	X	X					X	X	
 
Day 5: Procedures at discharge (Period 2) only.
 

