### 2.3.1. Risk Assessment

Potential Risk of Clinical Significance	Summary of Data/Rationale for Risk	Mitigation Strategy
Study Intervention(s) PF-07081532		
Gastrointestinal adverse reactions	
The potential risks are based on product labeling for injectable GLP-1R agonists (ie, liraglutide, exenatide, semaglutide and dulaglutide).
 
In addition, GI AEs, the majority of which were mild in severity, have been observed in the clinical program with PF-07081532.
	The single dose and dose level administered in this study minimize any potential risk.
Hypoglycemia	Clinical trials with injectable GLP-1R agonists have not demonstrated an increased risk for hypoglycemia. However, when administered in combination with anti-diabetic agents that are known to have an increased risk of hypoglycemia (such as insulin or sulfonylureas), an increased risk for hypoglycemia was observed.	The single dose and dose level administered in this study minimize any potential risk. The participants enrolled will not have diabetes and will not be receiving anti-diabetic agents. Study includes inpatient monitoring of the participants following administration of a single dose of the study intervention.
Increased heart rate	
Based on the product labeling for the injectable GLP-1R agonist liraglutide for obesity, mean increases in resting heart rate ranged 2 to 3 bpm in clinical trials, with some participants experiencing greater increases in resting heart rate, up to 10-20 bpm.
 
Following single dose administration of PF-07081532 in the completed FIH study, variable increases in heart rate were observed; the majority of individual values remained within normal ranges, and, throughout the study, no AEs or clinical symptoms related to vital sign parameters were reported.
	
The single dose and dose level administered in this study minimize any potential risk.
 
Study includes inpatient monitoring of the participants following administration of a single dose of the IP.

Other potential risks associated with long-term dosing of marketed GLP-1R agonists include thyroid C-cell tumors, pancreatitis, impairment in renal function, diabetic retinopathy complications,	These potential risks are based on product labeling for injectable GLP-1R agonists (ie, liraglutide, dulaglutide, exenatide and	The single dose and dose level administered in this study minimize any potential risk.

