#### 5.3.4. Activity

- Participants will not be permitted to engage in physically strenuous exercise (eg, heavy lifting, weight training, calisthenics, aerobics) for at least 48 hours prior to each blood collection for clinical laboratory tests while participating in the study; physical activity at an individual participant's normal pace is permitted;
  - In order to standardize the conditions on PK sampling days, participants will be required to refrain from lying down (except when required for BP, pulse rate, and ECG measurements) and eating during the first 4 hours after dosing.

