#### **8.3.3. Electrocardiograms**

Standard 12-lead ECGs utilizing limb leads (with a 10-second rhythm strip) should be collected at times specified in the [SoA](#) section of this protocol using an ECG machine that automatically calculates the HR and measures PR interval, QT interval, QTcF, and QRS complex. Alternative lead placement methodology using torso leads (eg, Mason-Likar) should not be used given the potential risk of discrepancies with ECGs acquired using standard limb lead placement. All scheduled ECGs should be performed after the participant has rested quietly for at least 5 minutes in a supine position.

To ensure safety of the participants, a qualified individual at the investigator site will make comparisons to baseline measurements within the respective period. Additional ECG monitoring will occur if a) a postdose QTcF interval is increased by  $\geq 60$  ms from the baseline **and** is  $> 450$  ms; or b) an absolute QT value is  $\geq 500$  ms for any scheduled ECG. If either of these conditions occurs, then 2 additional ECGs will be collected approximately 2 to 4 minutes apart to confirm the original measurement. If the QTcF values from these repeated ECGs remain above the threshold value, then a single ECG must be repeated at least hourly

until QTc values from 2 successive ECGs fall below the threshold value that triggered the repeat measurement.

If a) a postdose QTcF interval remains  $\geq 60$  ms from the baseline and is  $> 450$  ms; or b) an absolute QT value is  $\geq 500$  ms for any scheduled ECG for greater than 4 hours (or sooner, at the discretion of the investigator); or c) QTcF value get progressively longer, the participant should undergo continuous ECG monitoring. A cardiologist should be consulted if QTcF values do not return to less than the criteria listed above after 8 hours of monitoring (or sooner, at the discretion of the investigator).

In some cases, it may be appropriate to repeat abnormal ECGs to rule out improper lead placement as contributing to the ECG abnormality. It is important that leads be placed in the same positions each time in order to achieve precise ECG recordings. If a machine-read QTc value is prolonged, as defined above, repeat measurements may not be necessary if a qualified medical provider's interpretation determines that the QTcF values are in the acceptable range.

ECG values of potential clinical concern are listed in [Appendix 8](#).

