3.5.3. Vital Signs

Supine blood pressure (BP) and pulse rate (PR) will be measured at times specified in the SoA given in the protocol.

For both periods, the baseline measurement is the predose measurement on Day 1 in each period.

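### No pulse, blood pressure or ECG is scheduled between dosing and 96 h in either period, so the heart-rate mitigation and the vital-sign and ECG endpoint promise more than the schedule can deliver

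*Protocol*

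**What the plan says.** **Risk and mitigation.** The increased-heart-rate row of Protocol Section 2.3.1 states: "Following single dose administration of PF-07081532 in the completed FIH study, variable increases in heart rate were observed". It adds that most individual values stayed within normal ranges and that "no AEs or clinical symptoms related to vital sign parameters were reported". Two mitigations are listed. The first is the single dose and its level. The second is: "Study includes inpatient monitoring of the participants following administration of a single dose of the IP".

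**Endpoint.** Protocol Section 3 has one secondary endpoint with four components: treatment-emergent adverse events, laboratory abnormalities, vital signs and ECG parameters.

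**Schedule.** In SoA-Table 1 a single supine set of vital signs is taken at screening, on Day 1, on Day 5 and at early termination. The notes to that row read "Day 1 assessment: to be conducted pre-dose" and "Day 5 assessment: in Period 2 only". The ECG row has the same marks and equivalent notes. Neither row has an entry for Days 2 to 4.

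**Text that relies on post-dose readings.**
- Section 8.3.3 says that "a qualified individual at the investigator site will make comparisons to baseline measurements within the respective period" and attaches actions to post-dose QTcF thresholds.
- Section 9.3.2 says ECG, blood pressure and pulse data will be reviewed and summarized during the study to evaluate participants' safety.
- SAP 3.5.3, for vital signs, states: "For both periods, the baseline measurement is the predose measurement on Day 1 in each period". SAP 3.5.4 sets the same rule for ECG.
- Section 5.3.4 requires participants to "refrain from lying down (except when required for BP, pulse rate, and ECG measurements) and eating during the first 4 hours after dosing".

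**The concern.** The risk assessment describes an effect that came without symptoms and counts inpatient monitoring among its safeguards. The only safety monitoring that SoA-Table 1 runs through Days 1 to 4 is adverse event monitoring, and Section 2.3.1 reports no adverse events linked to the heart-rate changes already seen. Pulse, blood pressure and ECG are the measurements that would show such a change directly, and none is scheduled before 96 h.

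Two things are at stake. One is what the vital-sign and ECG components of the secondary endpoint can support: readings taken before dosing and once at about 96 h say little about an acute effect. The other is consistency. For a completer, the Period 1 baseline and the within-period ECG comparison have no scheduled Period 1 post-dose value to work on, and the ongoing review has no such value from either period until after the second dose.

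**Working it through.** This is a count from the schedule; no sample-size or error-rate figure is involved.

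**Inputs**
- Planned enrolment: about 20 participants, two doses each, 10 per sequence (Protocol Section 4.1 and Table 3).
- Vital-sign and ECG times: SoA-Table 1, as set out above.
- Minimum interval between doses: 6 days (SoA-Table 1).
- PK sampling times: SoA-Table 2.

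**Step 1: clock times.** Day 5 is (5 − 1) × 24 = 96 h after dosing, which agrees with the 96 h PK sample in SoA-Table 2. The minimum dosing interval is 6 × 24 = 144 h.

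**Step 2: readings per dose, if all 20 complete.** Total doses = 20 × 2 = 40.

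| Doses | Scheduled pulse, BP or ECG between 0 and 96 h | Scheduled reading at about 96 h | Next scheduled reading |
|---|---|---|---|
| Period 1 (20) | 0 | 0 | Period 2 pre-dose, at 144 h or later, used as the Period 2 baseline |
| Period 2 (20) | 0 | 20 | none |
| Total (40) | 0 | 20 | |

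A completer's first within-period post-dose reading therefore falls at least 144 + 96 = 240 h after the first dose, when both doses have been given.

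**Step 3: comparison of formulations.** In Sequence 1 the Period 2 treatment is Formulation B; in Sequence 2 it is Formulation A. The 20 readings at 96 h thus split into 10 after B and 10 after A, in different people. No participant has a scheduled within-period post-dose reading on both formulations.

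**Step 4: contact with participants in the same window.** SoA-Table 2 lists 15 post-dose PK samples per period. Eleven fall at or before 24 h (0.5, 1, 2, 3, 4, 6, 8, 10, 12, 16 and 24 h) and three more before 96 h (36, 48 and 72 h), giving 14 before 96 h. Participants are confined throughout.

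**Step 5: how much drug might remain at 96 h.** The visible documents give no half-life, so this is illustration only. With one-exponential decline counted from dosing, the fraction left is 2^(−96 / half-life):
- 12 h (assumed): 2^(−8) = 0.4%
- 24 h (assumed): 2^(−4) = 6.25%
- 28.8 h (assumed; 144 h / 5, that is, if the minimum washout were five half-lives): 2^(−3.33) = 9.9%

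The range is about 0.4% to 10% for an assumed half-life of 12 to 28.8 h. Under those assumptions a 96 h reading could show a late or persistent change but would not describe the effect near peak exposure.

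**The case against.** The case for the lean schedule has substance. Section 2.2.4.1 reports single doses up to 200 mg and multiple doses up to 180 mg once daily, with no clinically significant adverse trends in vital signs or ECG in either completed study. This trial gives 80 mg and exists to compare formulations. Section 2.3.1 lists the single dose and its level as the first mitigation and says most heart-rate values were normal, so the absence of related adverse events may mean the changes were small. Choosing not to characterize acute heart rate again is defensible. That stands, but it supports a narrower mitigation statement and endpoint, not the present wording.

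Unscheduled readings are also possible: Section 1.3 allows unplanned visits, Section 8.3 allows safety measurements at any time, and Section 8.3.2.1 permits extra blood pressure and pulse times. These are discretionary, and Section 8.3 links them to a perceived safety issue. A symptom-free rise would be unlikely to prompt one.

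Some of the apparent conflicts are mild. Section 5.3.4 is an exception clause and does not say that readings are scheduled in the first 4 h. The within-period baselines can serve early-termination or unscheduled readings in Period 1. They are provisions with no scheduled use in Period 1 for a completer, rather than outright contradictions.

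SAP 6.6.3 and 6.6.4 plan only to hold vital-sign and ECG data in the database, available on request. That makes a misleading summary table less likely. It also leaves two components of a stated endpoint without a planned summary, although Section 9.3.2 and SAP 6.6 provide for descriptive summaries of safety data where appropriate.

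Four stronger readings are tempting, and the documents do not support them.
- *Nothing is measured after the first dose.* The Period 2 pre-dose reading falls at 144 h or later, and early-termination readings exist.
- *The trial cannot detect a heart-rate effect.* A persistent change could appear at 96 h in Period 2, and discretionary readings remain possible.
- *At most 10% of the drug remains at 96 h.* This is not a bound. A longer half-life leaves more (36 h gives 2^(−96/36) = 15.8%), as does counting decay from the peak: an assumed Tmax of 6 h at 28.8 h gives 2^(−90/28.8) = 11.5%.
- *Heart-rate increases of the size quoted in Section 2.3.1 would go unseen.* Those figures come from another drug's labelling, not from single doses of this compound, so they do not measure what this schedule would miss.

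**Conclusion.** The point holds as a mismatch between the schedule and what the protocol says monitoring and the endpoint will provide. None of the 40 planned doses has a scheduled pulse, blood pressure or ECG between dosing and 96 h; 20 have one reading at about 96 h, and 20 have no within-period post-dose reading. With 14 completers instead of 20, the counts would be 0 of 28, 14 and 14.

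A transient symptom-free change in heart rate, blood pressure or QTcF would probably be missed. The vital-sign and ECG components cannot describe acute effects or support a within-participant comparison of formulations. In Period 1 no scheduled post-dose ECG can trigger the QTcF actions in Section 8.3.3 for a completer.

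The counts assume full completion and rest on the notes in SoA-Table 1, which name the days explicitly; the table's columns are partly broken in the text available. The redacted rows sit under the blood-sample heading and are taken not to contain these measurements. The counts do not depend on the half-life; only the illustration in Step 5 does. The primary PK comparison is unaffected.

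**What to change.** Reconcile SoA-Table 1 with the monitoring statement in Section 2.3.1, the within-period comparison in Section 8.3.3, the ongoing review in Section 9.3.2 and the per-period baselines in SAP 3.5.3 and 3.5.4. There are two consistent routes, and the choice is the sponsor's.

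1. The schedule supplies post-dose pulse, blood pressure and ECG readings within each period, at times the sponsor decides. The cost is a change to SoA-Table 1 and a few non-invasive readings in participants who are already confined and attended for PK sampling. The downside is some added supine time, which Section 5.3.4 allows for even in the first 4 h.
2. The schedule stays as it is. Section 2.3.1 then stops citing inpatient monitoring as the heart-rate mitigation. The vital-sign and ECG components are restated as pre-dose values and 96 h values in Period 2 only, and the study report draws no conclusion on acute heart-rate, blood pressure or QTcF effects. The cost is wording alone.

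Under either route, SAP 6.6.3 and 6.6.4 should say how these two components will be reported.
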